Section number and Change	Description of Change (the information added is shown in bold, and deleted information is shown as a strike-out)	Brief Rationale
Section 1.1 Synopsis and Section 3 Objectives and Endpoints (Table 1)	
 The Objective and Endpoint Table have been reorganized into Secondary Efficacy, Safety, and PK/PD Endpoints with further editorial revisions made to the content Text has been added that the primary efficacy, primary safety, and secondary efficacy endpoints will be assessed comparing Group A (CCI BID), B (CC 	Clarification of endpoints

Section number and Change	Description of Change (the information added is shown in bold, and deleted information is shown as a strike-out)	Brief Rationale
	
C BID), C (CCI BID) with Group D (Placebo)
 
 Footnote ^a was added to define OPP as the combination of the DYS and NMPP scores 	
Section 1.1 Synopsis	
Modify text in Rationale:
 
The primary efficacy endpoint will assess the efficacy of 3 dose levels of OG-6219 in change from Baseline Cycle (BC) in endometriosis-related overall pelvic pain (OPP) score (the weighted mean of the dysmenorrhea [DYS] pelvic pain score combined with the mean of and the non-menstrual pelvic pain score [NMPP; pain associated with micturition, defecation, ovulation, intercourse]) during the Treatment Cycle 3 (TRC3) compared to Placebo.
	Clarify the primary endpoint
Section 1.1 Synopsis and Section 9.4.2 Primary Endpoint Analysis	
Added sentence to include alternate error structures:
 
If nonconvergence is encountered, compound symmetry (CS) and first-order autoregressive AR(1) error structures will be considered.
	Agreement with FDA
Section 1.1 Synopsis and Section 9.4.3 Secondary Endpoint Analysis	
Added sentence to include alternate error structures:
 
If nonconvergence is encountered, CS and AR(1) error structures will be considered
	Agreement with FDA
Section 1.3 Schedule of Activities (footnote y), 2.3.1 Risk Assessment, Section 2.3.3 Overall Benefit Risks Conclusion, Section 8.3.4 Columbia Suicide Severity Rating Scale (C-SSRS)	
Deleted text:
 
Based on determination of positive C-SSRS results for suicidality and its severity, the participants will be discontinued from the study medication and referred to a specialist at the Investigator's discretion for further evaluation.
	Clarification that Study is not evaluating the severity
Section 2.3.1 Risk Assessment and Section 7.3 Criteria for Study Termination	
Clarification on
 
 DMC role independent safety monitoring and study stopping criteria to align with DMC charter 	Agreement with FDA
Section 5.2 Exclusion Criteria	
Exclusion criteria #9 has been modified:
 
Has a history of malignancy ≤ 5 years before signing informed consent except for adequately treated basal cell or squamous cell skin cancer or in situ cervical cancer. Note: Any history of hormonal sensitive malignancy (eg, breast
	Agreement with FDA

Section number and Change	Description of Change (the information added is shown in bold, and deleted information is shown as a strike-out)	Brief Rationale
	or ovarian cancers) excludes the participant.	
Section 6.7 Treatment Overdose	Clarified text on time frame to report an overdose	Agreement with FDA
Section 7.2 Participant Discontinuation/Withdrawal from the Study	
Updated bullet on ECG:
 
 ECG findings of QTcF prolongation of 500 CCI, or a change of >60 ms from the pre-dose ECG, based on the average of triplicate ECGs 
Added new bullets
 
 Safety recommendation based on DMC / investigator/ Sponsor assessment of AEs and AESI If the participant undergoes urgent surgical procedures for endometriosis-related pain. 	Agreement with FDA / clarification
Section 8.3.4 Columbia Suicide Severity Rating Scale (C-SSRS)	Added text to provide a threshold score using the Columbia Suicide Severity Rating Scale (C-SSRS) that subjects must reach for the investigator to discontinue the subject from clinical trial.	Agreement with FDA
Section 8.4.1 Time Period and Frequency for Collecting AE and SAE Information	Modified Table 7 Overdose row to clarify text on time frame to report an overdose.	Clarification and align with Section 6.7 Treatment Overdose
CCI	
 	
	Modified text CCI	Clarification
Section 9.4.7.1 Adverse Events	
Added text:
 
The timeframe for a TEAE after stopping the randomized treatment is 14 days.
	Clarification
Throughout the protocol	• Minor edits and corrections	Clarity

Amendment 04 (16-Jun-2023)

Overall Rationale for the Amendment:

The protocol OG6219-P001-03 has been amended to address Food and Drug Administration (FDA) questions and make clarifications to the protocol.

Section number and Change	Description of Change (the information added is shown in bold, and deleted information is shown as a strike-out)	Brief Rationale
Section 1.1 Synopsis (Overall Design), Section 3.0 Objectives and Endpoints (footnote to Table 1), Section 4.1 Overall Design, Appendix 1 Definitions	
Modified text
 
 TRC2 is the period between the first day of second menses after TRC1 end of BC to the day prior to first day of next menses, regardless of number of days. Phone Contact C is done during the menses. 
TRC3 or EOT is the period between the first day of third menses after TRC2 end of BC to either end after C completed cycles or CCI on study treatment, whichever occurs first.
	Clarification
1.3 Schedule of Activities	
Modified Footnote h
 
C: Participant must be CCI compliant with CCI to be randomized. (information to be provided by the eDiary portal).
	Clarification
	
Modified Footnote l
 
During the site study visit, the PRO should be completed prior to other types of study procedures, such as blood draws and physical examinations.
	Clarification
	
Modified Footnote v
 
C sample collection should to be collected within 12±4 hours of last dose of study medication. If not possible, the PK sample should be collected at C irrespective of the timing of the last study dose taken.
	Clarification that C PK sample must be taken even if not possible within stated window of time.
5.2 Exclusion Criteria	
Modified Exclusion Criterion #9.
 
Has a history of malignancy ≤5 years before signing informed consent except for adequately treated basal cell or squamous cell skin cancer or in situ cervical cancer.
	Agreement with FDA
	
Modified Exclusion Criterion #22 to exclude the use of CCI (per cycle).
 
Based on the known metabolism of OG-6219 there are no effects of alcohol, caffeine, or tobacco associated with study treatment. However, during the study participants are asked to refrain from:
	Response to FDA/ clarify use of CCI compounds

Section number and Change	Description of Change (the information added is shown in bold, and deleted information is shown as a strike-out)	Brief Rationale		
	
a) Excessive tobacco use and smoking (including excessive recreational marijuana CCI [REDACTED] based on Investigator's discretion. CCI [REDACTED] (ie, CCI [REDACTED] CCI [REDACTED])
			
5.2 Exclusion Criteria Table 2 Prohibited Medication, Contraceptive Devices and Other Substances	Table 2. Prohibited Medications: Analgesics Deleted text on CCI [REDACTED] Any prescribed CCI [REDACTED] for chronic pain management	Clarification to Table 2 for category of Other Prohibited Medications. Response to FDA/ clarify use of CCI [REDACTED] compounds		
	Prohibited Medications: Other Added CCI [REDACTED] CCI [REDACTED] compounds are permitted.	Response to FDA/ clarify use of CCI [REDACTED] compounds. Added cannabis to "other"		
5.3 Lifestyle considerations	Modified Note: Non-excessive CCI [REDACTED] CCI [REDACTED] CCI [REDACTED] compounds are permitted (usage must be recorded) CCI [REDACTED] (prescribed) for chronic pain use is prohibited. Refer to Table 2 for a list of prohibited medications.	Response to FDA/ clarify use of CCI [REDACTED] compounds		
Section 6.1 Study Treatments Administered	Modified Table 6. Non-Investigational Medicinal Products / Rescue Medication	Clarification to country-specific text to make protocol global. Deleted manufacturer as source may change depending on region/country		
	

Packaging and Labeling	
For US the product will be provided in commercial bottles. For EU the product will be provided in commercial blister packs.

All packs will be labeled as required per country requirements. Product will be provided in commercial packaging and will be labeled as required per country requirements.
	

Sourcing:	Provided centrally by the Sponsor. In special circumstances, may be	

		Packaging and Labeling	
For US the product will be provided in commercial bottles. For EU the product will be provided in commercial blister packs.
 
All packs will be labeled as required per country requirements. Product will be provided in commercial packaging and will be labeled as required per country requirements.

Packaging and Labeling	
For US the product will be provided in commercial bottles. For EU the product will be provided in commercial blister packs.
 
All packs will be labeled as required per country requirements. Product will be provided in commercial packaging and will be labeled as required per country requirements.
			
Sourcing:	Provided centrally by the Sponsor. In special circumstances, may be			

Section number and Change	Description of Change (the information added is shown in bold, and deleted information is shown as a strike-out)		Brief Rationale
		provided locally with prior approval from the Sponsor.	
	Manufacturer (Central Supply):	US: Glenmark Pharmaceuticals EU: KRKA, dd	
Section 8.5.1 Collection of Samples	Table 8. Schedule of Pharmacokinetic samples Modified footnote c C sample collection should to be collected within 12±4 hours of last dose of study medication. If not possible, the PK sample should be collected at C irrespective of the timing of the last study dose taken.		
Appendix 4	Modified Events Meeting the AE Definition Signs, symptoms, or the clinical sequelae of a suspected overdose of either study treatment or a concomitant medication. Overdose per se will not be reported as an AE/SAE unless it is an intentional overdose taken with possible suicidal/self harming intent. Such s should be reported regardless of sequelae. All overdose events must be reported in accordance with its seriousness including overdose taken with intentional suicidal/self-harming intent.		Clarification

Amendment 05 (07-Nov-2023)

Overall Rationale for the Amendment:

The protocol OG6219-P001-05 has been amended to address a Food and Drug Administration (FDA) question and make clarifications to the protocol.

Section number and Change	Description of Change (the information added is shown in bold, and deleted information is shown as a strike-out)	Brief Rationale
Study Schema	Change Screening period: Up to ~ 8 weeks Change Run-in period ~ 4 weeks Modified period between Visit 1 and Visit 2: Up to ~ 4 weeks Added to list of abbreviations: ~ = approximately	Clarification
Table 1.3 Schedule of Activities	Changed Screening on line 1 Up to ~12 weeks Added to list of abbreviations: ~ = approximately	Clarification
Section 5.2 Exclusion criterium #9	Has a no history of malignancy ≤5 years before signing informed consent (except for adequately treated basal cell or squamous cell skin cancer) before signing informed consent.	Agreement with FDA
Table 8. Schedule of Pharmacokinetic Sampling	Footnote a Morning dose is specified preferred for pre-witness dose.	Clarification
Section 2.2 and 10 References	Corrected cross-reference and updated reference list	Incorrect citation

## MODIFICATION HISTORY

Unique Identifier for this Version	Date of the Document Version	Author	Significant Changes from Previous Authorized Version
2.0	09JUN2025	PPD	This is the first version in the Organon SAP template. It is based on the IQVIA stable SAP 1.0, dated 15Nov2023, with some additions, modifications, and clarifications.

## 1. LIST OF ABBREVIATIONS

Abbreviation	Term
AE	Adverse event
AESI	Adverse event of special interest
ALT	Alanine aminotransferase
ANCOVA	analysis of covariance
AR (1)	first-order autoregressive 1
AST	Aspartate aminotransferase
BC	Baseline Cycle
BID	Twice a day
BMI	Body mass index
CI	Confidence interval
COVID-19	Coronavirus Disease 2019
CS	compound symmetry
C-SSRS	Columbia-Suicide Severity Rating Scale
CCI	
DMC	Data Monitoring Committee
DYS	Dysmenorrhea
E1	Estrone
E2	Estradiol
ECG	Electrocardiogram
eCOA	Electronic clinical outcome assessment
eCRF	Electronic case report form
eDiary	Electronic diary
EHP-30	Endometriosis Health Profile-30
ENR	All Participants Enrolled Analysis Set
EOS	End of Study
EOT	End of Treatment
ePRO	Electronic Patient Reported Outcome
EQ VAS	EQ Visual Analog Scale
CCI	
ERP	Endometriosis-related pain
FAS	Full Analysis Set
CCI	
hCG	Human chorionic gonadotropin
HRQoL	Health-related quality of life
ICH	International Council for Harmonisation of Technical Requirements for Pharmaceuticals for Human Use
C	
MFAS	Modified Full Analysis Set
NCA	Noncompartmental analysis
NMPP	Non-menstrual pelvic pain
NRS	Numeric rating scale

OPP	Overall Pelvic Pain (endometriosis-related)
PD	Pharmacodynamic
PGI-C	Patient Global Impression of Change
PGI-S	Patient Global Impression of Severity
PK	Pharmacokinetic
PP	Per Protocol Analysis Set
PRO	Patient-reported outcome
PROMIS	Patient Reported Outcomes Measurement Information System
PT	Preferred term
QTcF	Corrected QT interval according to CCI formula
SAE	Serious Adverse Event
CCI	
SC	Screening Cycle
SD	Standard deviation
SFAS	Safety Follow-up Analysis Set
SFC	Safety Follow-up Cycle
SoA	Schedule of Activities
TEAE	Treatment-emergent adverse event
T max	Time taken to reach the maximum concentration
TRC1	Treatment Cycle 1
TRC2	Treatment Cycle 2
TRC3	Treatment Cycle 3
TSH	Thyroid stimulating hormone
TVUS	Transvaginal ultrasound
ULN	Upper limit of normal
VAS	Visual Analog Scale
WPAI-Endometriosis	Work Productivity and Activity Impairment Questionnaire- Endometriosis

## 2. INTRODUCTION

[figure not shown]
The purpose of this statistical analysis plan (SAP) is to describe the methods, specifications, and conventions to be used in the analysis of efficacy and safety data for Protocol OG-6219-P001. The SAP is based on version 6.0 of the protocol. Results of the analyses described in this SAP will be included in the study report. Any post-hoc or unplanned analyses that are not described in this SAP will be clearly identified in the study report.

## 3. OBJECTIVES, ENDPOINTS, AND ESTIMANDS

The primary and secondary objectives and the corresponding endpoints are described in Table 1 (copied from the study protocol). The estimand and the analysis for the primary efficacy endpoint are described in Table 2. Estimands for secondary efficacy endpoints are defined using the same principle as for the primary efficacy endpoint.

**Table 1: Objectives and Endpoints (as described in the study protocol)**

Objectives	Endpoints
Primary Endpoints The following primary efficacy endpoint will be assessed comparing Group A (CCI BID), B (CCI BID), C (CCI BID) with Group D (Placebo)	

 
To evaluate the efficacy of 3 dose levels of OG-6219 (Group A, B, C) versus Placebo (Group D) in reducing OPP during TRC3, as measured by a NRS in the eDiary
 
	
 
Change from BC to TRC3 in the mean OPP scorea
 

The following primary safety endpoints will be assessed for Group A (CCI BID), B (CCI BID), C (CCI BID) and Group D (Placebo)	

 
To evaluate the safety and tolerability of OG-6219
 
	
 
Proportion of participants who experienced any AEs/SAEs
 
Abnormalities in clinical laboratory assessments, vital signs, and physical examination
 
Proportion of participants who prematurely discontinued study treatment due to AEs/SAEs
 

Secondary Efficacy Endpoints The following secondary endpoints will be assessed comparing Group A (CCI BID), B (CCI BID), C (CCI BID) with Group D (Placebo)	
1. To evaluate the efficacy of 3 dose levels of OG-6219 (Groups A, B, C) versus Placebo (Group	
 
Change from BC to TRC3 in the mean DYS score
 

D) in reducing DYS during TRC3, as measured by a NRS in the eDiary	
2. To evaluate the efficacy of 3 dose levels of OG-6219 (Groups A, B, C) versus Placebo (Group D) in reducing NMPP during TRC3, as measured by a NRS in the eDiary	
 
Change from BC to TRC3 in the mean NMPP score
 

3. To evaluate the efficacy of 3 dose levels of OG-6219 (Group A, B, C) versus Placebo (Group D) reducing dyspareunia during TRC3, as measured by a NRS in the eDiary	
 
Change from BC to TRC3 in the mean dyspareunia score
 

4. To evaluate the daily use of Sponsor provided rescue medication taken for ERP at TRC1, TRC2, and TRC3	
 
Change from BC to TRC1, TRC2, and TRC3 in the mean number of tablets of rescue medication for ERP
 
Change from BC to TRC1, TRC2, and TRC3 in the proportion of days participant has used rescue medication for ERP
 

5. To evaluate the change in the PGI-S Score at different time points	
 
Change in PGI-S Score from C to Phone Contact CCI
 

6. To evaluate the change in the PGI-C Score in different time points	
 
Percentage of participants with any improvement on the PGI-C at TRC1, TRC2, and TRC3
 

7. To evaluate the change in the EHP-30 domains (CCI ) from BC to TRC3	
 
Change from BC to TRC3 in the EHP-30 Domain Scores
 

Secondary Safety Endpoints	
8. To assess the incidence of clinically significant b changes from V1 to C in bone biomarkers: 	
 
Mean change from V1 to C in bone biomarker levels
 

9. To assess the incidence of any clinically significant b changes in laboratory parameters from V1 to CC 	
 
Proportion of participants with clinical parameters of significance from V1 to CCI
 

10. To assess vaginal bleeding pattern over the 3 menstrual cycles (TRC1, TRC2, and TRC3) as captured in the eDiary	
 
Mean change from BC to TRC1, TRC2, TRC3 in the number of days on period and number of days with irregular vaginal bleeding/spotting
 

11. To assess any potential change in the ECG parameters at CCI	
 
ECG parameter changes at CCI
 

Secondary PD / PK Endpoints	
12. To assess the change from CCI in serum hormone c concentrations	
 
Mean change from CCI in serum hormone levels
 

13. To assess any difference in serum hormone c concentrations at C between active treatment versus placebo	
 
Serum hormone levels at V5 comparing Group A (CCI BID), B (CCI BID), C (CCI BID) with Group D (Placebo)
 

Version Date: 09JUN2025

- Treatment Cycle 1 is the period between the first day of menses associated with treatment start (C) to the day prior to the first day of next menses, regardless of number of days.
- Treatment Cycle 2 is the period between the first day of second menses after end of BC to the day prior to first day of next menses, regardless of number of days.
- Treatment Cycle 3 or EOT is the period between the first day of third menses after end of BC to either end CCI on study treatment, whichever occurs first.
- Safety Follow-up Cycle is the period time between the first day after stopping study treatment during TRC3 and ends after 30 consecutive days.

- OPP score is defined as the combination of the DYS and NMPP scores in a cycle.
- Clinical significance is defined as any variation in physical findings or laboratory assessments that has medical relevance and may result in an alteration in medical care.
- CCI
- Intensive PK sampling is optional and applicable for subset of PK analysis set, where a separate consent would be provided.

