4. To evaluate the daily use of Sponsor provided rescue medication taken for ERP at TRC1, TRC2, and TRC3	
 Change from BC to TRC1, TRC2, and TRC3 in the mean number of tablets of rescue medication for ERP Change from BC to TRC1, TRC2, and TRC3 in the proportion of days participant has used rescue medication for ERP

Objectives	Endpoints
5. To evaluate the change in the PGI-S Score at different time points	• Change in PGI-S Score from C to Phone Contact CCI
6. To evaluate the change in the PGI-C Score in different time points	• Percentage of participants with any improvement on the PGI-C at TRC1, TRC2, and TRC3
7. To evaluate the change in the EHP-30 domains (CCI) from BC to TRC3	• Change from BC to TRC3 in the EHP-30 Domain Scores
Secondary Safety Endpoints	
8. To assess the incidence of clinically significant ^d changes from V1 to C in bone biomarkers: ○ CCI ○	• Mean change from V1 to C in bone biomarker levels
9. To assess the incidence of any clinically significant ^d changes in laboratory parameters from V1 to CCI	• Proportion of participants with clinical parameters of significance from V1 to CC
10. To assess vaginal bleeding pattern over the 3 menstrual cycles (TRC1, TRC2, and TRC3) as captured in the eDiary	• Mean change from BC to TRC1, TRC2, TRC3 in the percentage of days with vaginal bleeding
11. To assess any potential change in the ECG parameters at CCI	• ECG parameter changes at CCI
Secondary PD / PK Endpoints	
12. To assess the change from CCI in serum hormone ^b concentrations	• Mean change from CCI in serum hormone levels
13. To assess any difference in serum hormone ^b concentrations at C between active treatment versus placebo	• Serum hormone levels comparing Group A (CCI BID), B (CCI BID), C (CC BID) with Group D (Placebo)
14. To assess any difference in serum hormone ^b concentrations at C between active treatment versus placebo	• Serum hormone levels at V7 comparing Group A (CCI BID), B (CCI BID), C (CCI BID) with Group D (Placebo)
15. To assess the PK of orally administered OG-6219 and the active metabolite FOR-1011 using sparse and intensive ^c PK sampling.	
 • Plasma concentrations of OG-6219 and FOR-1011 at scheduled assessments using sparse PK sampling during the treatment period. • C_{max}, T_{max}, and AUC_{tau} for both OG-6219 and FOR-1011 on C and C for the population with intensive PK sampling
CCI	

CCI

Note: Refer below and to [Figure 1](#)

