## 8.7.6. Other Safety Assessments

### 8.7.6.1. VAGINAL BLEEDING PATTERN

Participants records the presence of bleeding or spotting CCI in the eDiary. The CCI questions to assess bleeding pattern in the eDiary are “1a: During the past 24 hours, did you have any vaginal bleeding or spotting? If the response is “Yes”, then the next question is, “1b: During the past 24 hours, have you been on your period?”.

The following endpoints will be calculated:

- Mean change from BC to TRC1, TRC2, TRC3 in the number of days on period
- Mean change from BC to TRC1, TRC2, TRC3 in the number of days with irregular vaginal bleeding/spotting (i.e. days when question 1a was answered yes and question 1b was answered no)

The definition of cycles for the above endpoints will be different from the definition used for efficacy endpoints. For the vaginal bleeding endpoints, cycles will be defined based on start of menses dates only as below:

- Screening cycle (SC) – starts at the start of menses associated with CCI and ends the day before the start of menses associated with CCI
- Baseline cycle (BC) – starts at the start of menses associated with CCI and ends at the day before the start of menses associated with CCI
- Treatment cycle 1 (TRC1) – starts at start of menses associated with visit 4 and ends the day before the start of menses associated with phone contact C (PC1).
- Treatment cycle 2 (TRC2) – starts at the start of menses associated with phone contact C and ends the day before the start of menses associated with CCI
- Treatment cycle 3 (TRC3) – starts at the start of menses associated with CCI and ends the day before the start of menses associated with CCI
- Safety follow-up cycle (SFC) – starts at the start of menses associated with CCI and ends the day before the start of menses associated with CCI

The following summaries will be provided for vaginal bleeding pattern:

- Observed values and change from BC in the number of days on period by treatment cycle

and by treatment group

- Observed values and change from BC in the number of days with irregular vaginal bleeding/spotting by treatment cycle and by treatment group

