## 10. CHANGES TO PROTOCOL-PLANNED ANALYSES

There were no changes to the analyses planned in the study protocol.

The study protocol did not include a description of the estimand. This has now been included in the SAP.

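### The SAP replaces the protocol's bleeding endpoint (percentage of days) with two raw day counts, labels them as the protocol's own, and does not analyse the percentage

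*SAP*

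**What the plan says.** **Protocol.** Endpoint 10, in both the Section 1.1 synopsis and Section 3.0 Table 1, is "Mean change from BC to TRC1, TRC2, TRC3 in the percentage of days with vaginal bleeding". It is one measure of any bleeding. The protocol does not say which days form the denominator.

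**SAP, endpoint table.** Section 3 says that "the corresponding endpoints are described in Table 1 (copied from the study protocol"), and the table title reads "Objectives and Endpoints (as described in the study protocol"). Endpoint 10 in that table is "Mean change from BC to TRC1, TRC2, TRC3 in the number of days on period and number of days with irregular vaginal bleeding/spotting".

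**SAP, analysis.** Section 8.7.6.1 derives two counts per cycle. The first is "Mean change from BC to TRC1, TRC2, TRC3 in the number of days on period"; the second counts days on which the participant reported bleeding or spotting but was not on her period. Both are summarised descriptively. On the time window it says: "For the vaginal bleeding endpoints, cycles will be defined based on start of menses dates only as below".

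**SAP, declared changes.** Section 10 states: "There were no changes to the analyses planned in the study protocol". The only addition it mentions is the estimand. Section 2 states: "The SAP is based on version 6.0 of the protocol".

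**The concern.** There are two problems.

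1. **Traceability.** A pre-specified safety endpoint has been changed in two ways: a percentage became a count, and one any-bleeding measure became two components. The SAP presents the result as the protocol's text. A reader of the study report would have no indication that the protocol's endpoint was dropped.

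2. **Missing diary days.** A bleeding day that was never entered cannot be counted. If entries become sparser after BC, the counts fall even when bleeding does not. For a safety endpoint that is the unfavourable direction, because a real increase could be masked.

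**Working it through.** **Is it a version difference or a redaction?** The SAP names protocol version 6.0. The current protocol text (Amendment 06) still has the percentage in both places, and no redaction touches the wording. Neither explains the mismatch.

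**Is the percentage computed elsewhere in the SAP?** No. Section 8.7.6.1 lists the two counts and their changes from BC, and no other section analyses bleeding days. The numerator can be recovered: period days and irregular days together make up all days with reported bleeding. What is missing is the denominator.

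**How are other diary endpoints handled?** SAP 8.3.3 divides overall pelvic pain by the days with a score. SAP 8.4.1 divides rescue tablets and rescue days by the days with a reported value. Section 8.7.6.1 has no such denominator and no minimum number of diary days, and SAP 8.1.5 rules out imputation.

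**Size of the missing-day effect.** The plan gives no expected value, power or sample size for bleeding, so there is no stated figure to reproduce. All bleeding and completeness values here are assumptions: a 28-day cycle, 5 period days and 3 irregular days in every cycle, and entries missing at random. The expected count is true days × completeness, so the false change is true days × (completeness in the treatment cycle − completeness in BC).

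| Completeness, BC → treatment cycle | Period days | Irregular days | % of reported days |
|---|---|---|---|
| 95% → 90% | 5 × (−0.05) = −0.25 | 3 × (−0.05) = −0.15 | 28.6 → 28.6 |
| 95% → 85% | −0.50 | −0.30 | 28.6 → 28.6 |
| 95% → 80% | −0.75 | −0.45 | 28.6 → 28.6 |
| 95% → 70% | −1.25 | −0.75 | 28.6 → 28.6 |

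The percentage is stable because completeness cancels: (8 × c) / (28 × c) = 28.6% for any c. That requires the denominator to be reported days. With all 28 cycle days as denominator it would go from 8 × 0.95 / 28 = 27.1% to 8 × 0.80 / 28 = 22.9%, so the denominator has to be written down.

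**Comparison with placebo.** If every arm falls from 95% to 80%, each shows −0.75 period day and the difference is 0. If placebo falls to 90% and an active arm to 80%, the false difference is −0.75 − (−0.25) = −0.50 day.

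**Cycle length.** The expected range is 21 to 32 days (protocol Section 4.1). Assume 5 period days per cycle and irregular bleeding on 10% of the other days.

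| | 21 days | 32 days |
|---|---|---|
| Period-day count | 5 | 5 |
| Irregular-day count | 0.10 × 16 = 1.6 | 0.10 × 27 = 2.7 |
| Period days as % of cycle | 5/21 = 23.8% | 5/32 = 15.6% |
| Any bleeding as % of cycle | 6.6/21 = 31.4% | 7.7/32 = 24.1% |

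The irregular-day count grows with cycle length and the period-day count does not. The percentage also moves.

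**Days after last dose.** SAP 8.1.6, under general methodology, assigns days after the last treatment day to the safety follow-up cycle only. Section 8.7.6.1 defines bleeding cycles by menses dates alone and says that they differ from the efficacy cycles. The two sections can be read against each other.

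**The case against.** The best defence is that separating period days from irregular bleeding is clinically more informative than one pooled percentage, and that a period-day count is steadier across cycle lengths. Both points stand, and they are the reason to keep the counts. The endpoint is also secondary, descriptive and without alpha, and all data are listed. That limits the consequence but does not make the label or Section 10 correct.

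Four stronger readings are tempting, and the documents do not support them.

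- **Counts must drift down from BC.** The compliance threshold in inclusion criterion 11 covers the screening and baseline cycles only, and no threshold is stated for later cycles. But the schedule of activities checks diary compliance during treatment, reminders are sent (protocol 8.2.1), and inability to comply with the diary is a listed reason for discontinuation (protocol 7.2). A fall is possible, not built in.
- **The percentage cures everything.** It removes the missing-day effect only if entries are missing at random and reported days are the denominator. It does not remove cycle-length dependence.
- **Off-drug days are counted as treatment-cycle days.** SAP 8.1.6 says otherwise. What can be shown is an unresolved conflict between two sections.
- **Cutting bleeding cycles at last dose is the remedy.** Cycles start with menses, so truncation leaves fragments heavy in period days. A participant with a 5-day period who stops on cycle day 10 would score 5/10 = 50%, against 5/28 = 17.9% for a full 28-day cycle, with no change in bleeding.

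**Conclusion.** The undeclared replacement is certain from the text: the protocol's endpoint 10 is not analysed, the table that omits it is described as a copy, and Section 10 is wrong on this point.

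The lack of a reported-day denominator is also certain. Its numerical effect is conditional. With an assumed 5-day period and completeness falling from 95% to 80%, the period-day count falls by 0.75 day with no real change; at 70% it falls by 1.25 days. The documents give no completion rates, and the entry threshold is redacted. A biased comparison with placebo additionally needs completeness to differ between arms.

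This should be corrected before the results are reported. It does not affect the primary analysis or any test in the plan.

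**What to change.** 1. Analyse the protocol percentage as endpoint 10: per cycle, 100 × (days with bleeding reported) / (days with a bleeding entry). State the denominator explicitly, following the SAP's own rule for rescue medication. The protocol leaves it open, so this is a specification and not a restoration of protocol wording.
2. Keep the two counts as additional summaries, shown with the number of diary days and the cycle length for each cycle and arm.
3. Correct the description of SAP Table 1 as a copy, and list the added counts in Section 10.
4. Reconcile SAP 8.1.6 with the menses-only cycles of 8.7.6.1: say where days after last dose belong for the bleeding endpoints and how partial cycles are handled. Do not simply truncate at last dose.

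The cost is SAP wording and one derived denominator from data already collected.
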